**Schema**

For Patients with Probable Alzheimer's Disease based on NINCDS-ADRDA Criteria and having MMSE scores of between 10 - 20	
Number of Patients	30
Randomization	N/A
Screening/Baseline Testing	
The following tests/evaluation will be completed prior to initiation of treatment
 
 
1) MMSE
 
2) ADAS-Cog
 
3) History and Physical
 
4) Amyvid PET Scan
 
5) Toxicity Evaluation using CTC version 5.0/RTOG for following sites Skin, Eye, Ear and CNS
 
6) QOL-AD and QUALID assessment
 

Imaging Requirements	An Amyvid PET Scan will be required prior to treatment and at 4 months following completion of therapy. These scans will be read by the study designated board certified nuclear radiologist.
Treatment Procedure	Patients will receive whole brain irradiation using standard external beam techniques. The initial 15 patients will be treated at Dose Level 1 (5 x 200 cGy). If after the last patient in the first treatment group has been followed for 12 months and there have been no events that cause stoppage of the trial, the second group of patients will be enrolled at Dose Level 2 (10 x 200 cGy). All patients will receive 1 treatment per day on consecutive days excluding weekends
Trial Visits and Follow-Up	All patients will be followed as per Study calendar. Scheduled post treatment visits are at 6 weeks 3, 4, 6, and 12 months

Stopping Rules	
This Study will be stopped for any of the following reasons
 
 
1) Any patient death attributed to treatment
 
2) Any patient who develops a Grade IV adverse event
 
3) More than 3 of 15 patients who develop a Grade 3 adverse event as per CTCAE v.5.0 in either group
 
4) 50% or more of patients in either group have no change or increase in amyloid based on Amyvid PET Scan
 
5) 5 patients that show greater than 4 point deterioration in MMSE in two consecutive cognition evaluations
 
6) 5 patients that show mean increases greater than 7 on ADAS-Cog scale.
 

Data Safety Monitoring Board (DSMB)	
This trial will utilize a DSMB consisting of three physicians and one biostatistician who are not directly involved in the trial but who have expertise in radiation, Alzheimer's management, or both.
 
They will meet monthly to review all new data that has been collected on any patient under treatment or in follow up and report quarterly to the IRB.

Treatment Groups	
There will be two dose levels:
 
 
1) 5 x 200 cGy
 
2) 10 x 200 cGy
 

Trial Duration	12 month follow up following completion of therapy for each individual.

## Abbreviations

AD	Alzheimer' Disease
A $\beta$	amyloid-beta
FDA	Food and Drug Administration
A $\beta$ PP	amyloid- $\beta$ precursor protein
BBB	blood-brain barrier
RT	radiation therapy
Gy	Gray
PCI	Prophylactic cranial irradiation
H&E	hematoxylin and eosin
BED	biological effective dose
SD	standard deviation
LET	linear energy transfer
NINCDS-ADRDA	National Institute of Neurological and Communicative Disorders and Stroke and the Alzheimer's Disease and Related Disorders Association
PET	positron emission tomography
CTCAE v. 4.0	Common Toxicity Criteria for Adverse Events
RTOG/EORTC	Radiation Therapy Oncology Group/European Organization for Research and Treatment of Cancer
MMSE	Mini Mental State Examination
ADAS-Cog	Alzheimer's Disease Assessment Scale-cognitive subscale
QOL-AD	Quality of Life- Alzheimer's Disease
QUALID	Quality of Life in Late Stage Dementia
SCLC	small cell lung cancer
IRB	Institutional Review Board
DSM-IV	Diagnostic and Statistical Manual of Mental Disorder, Fourth edition
CBCT	cone beam computed tomography
HVL	half-value layer
DSMB	Data Safety Monitoring Board

## 1.0 Background and Rationale

### 1.1 Current and Future Incidence of Alzheimer's Disease

Alzheimer's disease (AD) is the most common form of dementia among the elderly and affects over five million individuals in the United States [1]. Approximately 200,000 people younger than 65 years with AD comprise the younger onset AD population; 5 million are age 65 years or older. By mid-century, fueled in large part by the baby boom generation, the number of people living with AD in the United States is projected to grow by about 9 million [2]. In 2010, official death certificates recorded 83,494 deaths from AD, making AD the sixth leading cause of death in the United States and the fifth leading cause of death in Americans aged 65 years or older. Between 2000 and 2010, the proportion of deaths resulting from heart disease, stroke, and prostate cancer decreased 16%, 23%, and 8%, respectively, whereas the proportion resulting from AD increased 68%. The actual number of deaths to which AD contributes (or deaths *with* AD) is likely much larger than the number of deaths *from* AD recorded on death certificates. In 2014, an estimated 700,000 older Americans will die with AD, and many of them will die from complications caused by AD [2].

Data from the Framingham Study were used to estimate lifetime risks of AD and any dementia [3]. The study found that 65-year-old women without dementia had a 20% chance of developing dementia during the remainder of their lives compared with a 17% chance for men. For AD specifically, the estimated lifetime risk at the age of 65 years was nearly one in six (17.2%) for women compared with nearly 1 in 11 (9.1%) for men. There is a clear relationship between increasing age and AD. The number of Americans surviving into their 80s, 90s, and beyond is expected to grow dramatically because of advances in medicine and medical technology, as well as social and environmental conditions. By 2030, the segment of the US population aged 65 years and older is expected to grow dramatically, and the estimated 72 million older Americans will make up approximately 20% of the total population.

### 1.2 Pathophysiology of Alzheimer's Disease

The pathophysiology of AD develops over many years. The major pathological hallmarks are the accumulation of senile amyloid-beta (A $\beta$ ) plaques [4,5] and the development of insoluble neurofibrillary tangles of tau protein [6]. A $\beta$  is produced by the proteolytic cleavage of A $\beta$  precursor protein (A $\beta$ PP) by  $\beta$ - and  $\gamma$ -secretases [7,8]. The abnormal processing and accumulation of A $\beta$  initiates a cascade of events that culminates in neuronal damage and dementia [9-12]. In late-onset AD, the amount of A $\beta$  that accumulates can be ~100–200-fold higher than normal [13]. The most recognized hypothesis [14] proposes that AD can be attributed to an imbalance between the production and clearance of A $\beta$ , although A $\beta$  clearing is not necessarily accompanied by cognitive improvement [15,16]. A $\beta$  folding [17] and neuro-inflammation [18] may also be important in AD progression. The AD inflammatory response is associated with both neurodegeneration and neuronal survival with tissue repair [18-21].

### **1.3 Current Treatments for Alzheimer's Disease**

The U.S. Food and Drug Administration (FDA) has approved five medications to treat the symptoms of Alzheimer's disease. donepezil, rivastigmine, galantamine, memantine and the combination of donepezil and memantine. The first three are acetylcholinesterase inhibitors that enhance the neurotransmission of acetylcholine in the brain, which is thought to be essential for cognition. There are many other strategies that have been studied for AD treatment including immunologic, nutraceutical, mitochondrial, phosphodiesterase, 5-HT6 receptor agonists and stem cell-based treatments [22]. The results from large-scale randomized clinical trials of pharmacological agents have been modest and it is clear that AD has multiple risk factors and is likely to have multiple pathogenic pathways. AD is not a one-gene, one-protein disease and should be attributed to a network of interactions between genes, proteins, organelles, cells, neurotransmitters, and the environment. Those disease-modifying agents currently being developed typically target one hypothesis and one protein. Thus, it is clear that a single drug for the successful treatment of AD is not yet available.

### **1.4 Background and Rationale for Radiation Treatment of AD**

Eliminating amyloid- $\beta$  has been advocated as a beneficial treatment strategy for AD patients, and anti-amyloid therapies remain a rational approach for preventing or delaying AD [23]. Amyloid- $\beta$  is produced by the proteolytic cleavage of amyloid- $\beta$  precursor protein (A $\beta$ PP) by  $\beta$ - and  $\gamma$ -secretases and many novel pharmaceuticals are being developed to prevent the initial cleavage of A $\beta$ PP [24,25]. The blood-brain barrier (BBB) has limited or thwarted the success of many of these agents either by preventing the drugs from initially crossing into the brain, or by ensuring the rapid removal of those drugs that can cross the BBB [26]. Delivery of an anti-amyloid therapy that is independent of the blood-brain barrier would be a promising new approach. One strategy not investigated previously for the treatment or elimination of amyloid- $\beta$  plaques associated with AD is ionizing radiation therapy (RT). Radiation therapy has been shown previously to reduce amyloid-like deposits in extra-cranial disease sites [27-29].

Ionizing RT has not been considered previously for AD patients because of the potential to exacerbate cognitive impairment. The potential for side effects from brain RT are dependent on the total radiation dose given. Total doses of 30–60 Gy given in 2 Gy fractions can produce macroscopic tissue destruction [30] and impair cognition [31-35]. However, only minimal cognitive effects are produced (minor compared with the normal cognitive decline associated with AD) if the total dose remains low and critical brain structures are spared using image-guided RT. The severity of cognitive impairment depends upon the dose delivered to the medial temporal lobes, the site of the hippocampus [36]. Changes are evident using single doses of 5 Gy or higher [32-34], although 2 Gy produced no cognitive deficit [34]. Prophylactic cranial irradiation (PCI) [37], to a total dose of 12–20 Gy in 2 Gy fractions given daily, has become the standard-of-care for selected groups of adult patients with small cell lung cancer and in pediatric leukemia patients to decrease CNS relapse[38], with no [39,40], mild [41,42] or moderate [43] cognitive impairment. Moreover, whole brain RT can lead to the recruitment of protective glial cells that would be beneficial in an AD patient [33], and the use of recognized protectors or mitigators of RT damage would provide additional clinical safeguards [33,44-48]. Therefore, RT is a potential novel treatment option for AD that could be rapidly and

inexpensively implemented, especially when compared to the time needed and costs associated with developing new pharmaceuticals that are often only partially effective.

[figure not shown]
### **1.5 Preclinical Data Utilizing Radiation Treatment for Alzheimer's Disease**

#### ***1.5.1 Effect of Radiation on Amyloid $\beta$ Plaque Burden***

The preclinical studies described in section 1.5.1 and 1.5.2 have been accepted for publication [49]. We used an established double transgenic model of AD namely, male B6.Cg-Tg (APPswe,PSEN1dE9)85Dbo/J mice. These mice express a chimeric mouse/human amyloid precursor protein (Mo/HuAPP695swe) and a mutant human presenilin 1 (PS1-dE9), both directed to CNS neurons. Both mutations are associated with early-onset Alzheimer's disease. In initial proof-of-principle experiments, 30 6-month-old mice were randomized into groups (n=3-6 per group) and the right half of the brain X-irradiated at room temperature with either a single dose of 5Gy, 10Gy or 15Gy and sacrificed either 2, 4 and 8 weeks later. In subsequent studies, animals were treated with three different low-dose schedules 1Gy $\times$ 10, 2Gy $\times$ 5 or 2Gy $\times$ 10. To assess the effects of treatments, coronal tissue sections (5 $\mu$ m) were cut from the harvested, formalin-fixed brains and mounted for antibody-specific immunohistochemistry of amyloid- $\beta$  (A $\beta$ ), standard hematoxylin and eosin (H&E) for morphology and Nissl staining to assess neuronal cell density. Three

stained coronal slices per mouse were analyzed to compare the number and size of beta-amyloid plaques in the irradiated versus untreated sides of the brain. A $\beta$  plaques were counted and analyzed using an image analysis approach. By using a hemi-brain irradiation approach, we were able to overcome the inherent variability in A $\beta$  plaques between animals as each animal served as its own control by comparing the irradiated side of the brain to the unirradiated side of the same brain (Figure 1). The percent change in plaque number between the irradiated and unirradiated side of the brain after Hemi-Brain Radiotherapy (HBRT) therefore indicated the true effect of the radiation treatment

irrespective of the initial number of plaques that were present. The largest percent decrease in A $\beta$  plaques was seen with the 5x2 Gy dose regimen (Table 1). Moreover, the size of the remaining A $\beta$  plaques was smaller in the irradiated sides of the brain. At 4 weeks, the average decrease in A $\beta$  plaque size was 13.8% (p=0.045), 17.2% (p= 0.021), 27.6% (p=0.011), 29.3% (p=0.005) and 28.7% (p=0.049) for animals given 5 Gy, 10 Gy and 15 Gy, 10x1 Gy and 5x2 Gy hemi-brain irradiation respectively. Single dose treatments and fractionated treatments can be mathematically

**Figure 1:** The right side in this coronal image was irradiated [RT]. The left side was not exposed [no-RT]. Fewer plaques are present on the RT side of the brain. 5x2 Gy was given and assessed at 4 weeks post RT.

	5Gy		10Gy		15Gy		1Gyx10		2Gyx5		2Gyx10		
Time	Mean	SD	Mean	SD	Mean	SD	Mean	SD	Mean	SD	Mean	SD	
2 weeks	26.2	23.9	32.8	12.5	41.2	17.6							
4 weeks	29.3	13.1	45.7	33.6	56.9	33.2	50.6	3.2	71.8	23.4	78.5	14.5	
8 weeks	21.5	14.2	54.2	19.3	68.2	14.3							

**Table 1:** Mean percent decrease in the number of A $\beta$  plaques in the whole brain (cortex and hippocampus regions combined) for each **hemi-brain** RT regimen and assessment time. The size of the reduction in A $\beta$  is dependent on the RT dose and assessment time. The percent decrease was calculated for each animal individually by comparing the plaque count between the irradiated and unirradiated sides of the brain, and then the mean and standard deviation (SD) percent reductions were calculated for each treatment group consisting of 3 animals. This analysis method is independent of the initial number of A $\beta$  plaques present.

compared using the biological effective dose (BED) [50]. A larger percentage reduction is evident after the low-dose fractionated regimes compared with the single dose treatments. For example, a 29.3% (SD $\pm$ 13.1) reduction in A $\beta$  plaques was seen after a 5Gy single dose (BED=17.5Gy) compared with 50.6% (SD $\pm$ 3.2) and 70% (SD $\pm$ 23.4) reductions after the 1Gyx10 (BED=15Gy) and 2Gyx5 (BED=20Gy) respectively. The most effective schedule was 2Gy x 10 (BED=30Gy) where the plaque reduction was 78.5%. This BED comparison clearly demonstrates a more pronounced reduction in A $\beta$  plaque number with fractionation compared with larger single dose treatments.

All radiation treatments were well-tolerated and no post-radiation behavioral changes were observed, suggesting negligible or limited radiation-induced effects on normal brain tissues over the time course of the experiment. In addition, histological examination of the H&E stained tissue sections indicated no evidence of a significant decrease in cell density and no compelling evidence of significant cellular necrosis. No signs of devitalization, malacia or spongiosus or classic acute or chronic inflammatory features were seen in the tissue sections, confirming that the radiation doses were insufficient to produce notable cellular effects on normal tissues. A comparison of neuronal cell density from Nissl stained brain tissue sections indicated little difference in number of neuronal cells between the irradiated right-side and unirradiated left side of the brain, irrespective of dose or time post-treatment.

### 1.5.2 Effect of Radiation on Cognitive Performance

The histology data suggested that there were no microscopic effects of low dose radiation on the brain; this was taken further in the next phase of the research by studying cognitive function after low dose radiation treatment. These experiments were

[figure not shown]

Figure 2: 64-week-old whole-brain irradiated animals had significantly lower numbers of A $\beta$  plaques at 8-9 weeks after irradiation with 5 x 2 Gy than sham-treated animals.

performed in collaboration with an independent group of Psychology scientists in a strict blinded-fashion and treatment groups were unknown to the individuals conducting the cognitive testing. 64-week old male mice were given **whole-brain** irradiation (n=19) or sham-treated exposures (n=14) and evaluated 8 weeks later. Figure 2 shows the plaque burden of these animals. The average number of plaques in the unirradiated cortex of the brain at 73 weeks was 3787 (SD  $\pm$ 1552; n=14), with a numerical range of 1777-6554 and median of 3560. The average number of plaques in the cortex of an irradiated brain was 2642 (SD  $\pm$ 1379; n=19), with a numerical range of 512-4695 and median of 2677. Daily irradiated with 2 Gy for five consecutive days with reduced the mean number of plaques (p=0.036). Average plaque size also decreased following irradiation from 42.95 $\mu$ M (SD  $\pm$ 12.8) to 14.52  $\mu$ M (SD  $\pm$ 11.6). Spatial learning and memory were assessed in a Morris maze protocol over two 5-day periods, once before treatment (5 days prior to RT) and once after treatment (8 weeks after RT). The mice were trained to locate a platform submerged in a pool of opaque water (22°C $\pm$ 1°C) in 3 trials/day with a 30-min inter-trial interval over 5 consecutive days. Latency to find the platform was measured. Eight weeks following RT mice were retested. Prior to whole-brain irradiation, the group of animals to be treated with 2Gy $\times$ 5 (*Mean (M)* = 48.67 secs, *SD* = 15.63 secs) and the untreated group (*M* = 58.07, *SD* = 23.34) did not differ significantly in latency to find the platform across trials on the final testing day (day 5), p =0.399. Following irradiation, the treated mice showed no deficits in spatial learning and memory relative to the control group prior to treatment, again suggesting negligible or limited radiation-induced effects on normal brain functioning. Conversely, the treated group displayed significantly reduced latencies (*M* = 30.96, *SD* = 17.64) compared to the untreated group (*M* = 53.93, *SD* = 14.92) across trials on day 5, *t*(11) = 2.41, p = 0.03. This difference was not due to difference in swimming velocity (p=0.545) or baseline ambulatory velocity (p=0.165).

In summary, we have demonstrated that external beam low-LET X-irradiation produces a significant reduction in amyloid- $\beta$  plaques, pathologies causatively linked with AD. From our data we cannot determine if the radiation treatment is directly or indirectly eliminating the plaques or alternatively preventing the production and deposition of new amyloid- $\beta$  plaques. However, these data provide preliminary evidence that these radiation treatments do not negatively affect cognitive function and may even improve some aspects of cognition.

## 2.0 Objectives and Endpoints

### 2.1 Primary Objectives

In this proposed study we will assess the safety and toxicity/adverse events associated with the use of low dose fractionated whole brain irradiation in patients who have been diagnosed with probable Alzheimer's disease according to NINCDS-ADRDA criteria.

### 2.2 Secondary Objectives

- 1) Investigate whether or not the intervention with low dose whole brain irradiation changes the recognized progression of Alzheimer's disease through cognitive testing.
- 2) To monitor quality of life parameters.

- 3) Collect information from AMYvid® PET Scans before and after treatment to investigate if there is any correlation between neurocognitive/quality of life scores and changes in amyloid plaque size, number and location.

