### **2.4 Secondary Endpoints**

- 1) Neurocognitive testing will be used to assess changes in cognitive function using the MMSE and ADAS-Cog. The tests will be administered by an appointed, trained site professional at baseline and at 6 weeks, 3 months, 6 months, and 12 months during follow-up.
- 2) Quality of life will be monitored via questionnaires completed by the patient prior to the start of irradiation and at 6 weeks, 3 months, 6 months, and 12 months during follow-up. Specific questionnaires include the QOL-AD and QUALID, which have been established as sensitive measures of various parameters of quality of life.
- 3) A pretreatment and post treatment (4 months) Amyvid PET/CT scan will be carried out to determine if there are any correlations between neurocognitive /QOL test results and amyloid number, size and location and changes after treatment.

[figure not shown]

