### **3.6 Pretreatment Amyvid PET/CT Scan**

Amyvid (Florbetapir-F18) is a radiopharmaceutical compound approved by the FDA as a diagnostic tool in AD. Amyvid binds to amyloid- $\beta$  with a half-life of 110 minutes. The tracer significantly accumulates more in brains of patients with AD particularly in the regions known to be associated with amyloid- $\beta$  deposits [57]. A negative Amyvid scan indicates sparse to no amyloid- $\beta$  neuritic plaques and is inconsistent with a neuropathological diagnosis of AD at the time of image acquisition. A positive Amyvid scan indicates moderate to frequent amyloid neuritic plaques; neuropathological examination has shown this amount of amyloid neuritic plaque is present in patients with AD, but may also be present in patients with other types of neurologic conditions as well as older people with normal cognition. Amyvid will be administered at a dose of 370 MBq (10 mCi) administered as a single intravenous bolus in a total volume of 10 mL or less. Following the injection, an intravenous flush of 0.9% sterile sodium chloride will be administered. A 10-minute PET image will be acquired starting 30 to 50 minutes after Amyvid intravenous injection. The patient will be supine and the head positioned to center the brain, including the cerebellum, in the PET scanner field of view. Reducing head movement with tape or other flexible head restraints may be employed. Image reconstruction will include attenuation correction with resulting transaxial pixel sizes between 2 and 3 mm. Amyvid images will be interpreted only by the study designated board certified nuclear radiologist. The current guidelines for display and interpretation of Amyvid images will be followed (Appendix VII). Briefly, images will be displayed in the transaxial orientation with access as needed to the sagittal and coronal planes. In reviewing the images, all transaxial slices of the brain will be included using a black-white scale with the maximum intensity of the scale set to the maximum intensity of all the brain pixels. The brain slice with the highest levels of image contrast (highest radioactivity signals for Amyvid uptake) will be located and the contrast adjusted appropriately. Image interpretation will be initiated by displaying slices sequentially from the bottom of the brain to the top. Image interpretation is based upon the distribution of radioactive signal within the brain; clinical information is not a component of the image assessment. Images are designated as positive or negative by comparing the radioactivity in cortical gray matter with activity in the adjacent white matter.

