### **3.11 Post-treatment Amyvid PET/CT Scan**

A second Amyvid (Florbetapir-F18) PET scan will be done at 4 months after completion of treatment. Amyvid will be administered at a dose of 370 MBq (10 mCi) administered as a single intravenous bolus in a total volume of 10 mL or less. Following the injection, an intravenous flush of 0.9% sterile sodium chloride will be administered. A 10-minute PET image will be acquired starting 30 to 50 minutes after Amyvid intravenous injection. The patient will be supine and the head positioned to center the brain, including the cerebellum, in the PET scanner field of view. Reducing head movement with tape or other flexible head restraints may be employed. Image reconstruction will include attenuation correction with resulting transaxial pixel sizes between 2 and 3 mm. Amyvid images will be interpreted only by the study designated nuclear radiologist. Analysis will be carried out as previously described. Pre- and post-radiation scans will be presented in random order, with the nuclear radiologist blinded to the order of presentation and patient identity or clinical details.

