### 2.4 Image Display and Interpretation

Amyvid images should be interpreted only by readers who successfully complete a special training program [*see Warnings and Precautions (5.1)*]. Training is provided by the manufacturer using either an in-person tutorial or an electronic process.

The objective of Amyvid image interpretation is to provide an estimate of the brain β-amyloid neuritic plaque density, not to make a clinical diagnosis. Image interpretation is performed independently of a patient's clinical features and relies upon the recognition of unique image features.

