#### *Image Interpretation*

Image interpretation is based upon the distribution of radioactive signal within the brain; clinical information is not a component of the image assessment [*see Warnings and Precautions (5.1)*]. Images are designated as positive or negative by comparing the radioactivity in cortical gray matter with activity in the adjacent white matter. This determination is made only in the cerebral cortex; the signal uptake in the cerebellum does not contribute to the scan interpretation (for example, a positive scan may show retained cerebellar gray-white contrast even when the cortical gray-white contrast is lost).

[figure not shown]
- *Negative scans* show more radioactivity in white matter than in gray matter, creating clear gray-white contrast.
- *Positive scans* show cortical areas with reduction or loss of the normally distinct gray-white contrast. These scans have one or more areas with increased cortical gray matter signal which results in reduced (or absent) gray-white contrast. Specifically, a positive scan will have either:
  - Two or more brain areas (each larger than a single cortical gyrus) in which there is reduced or absent gray-white contrast. This is the most common appearance of a positive scan.  
*or*
  - One or more areas in which gray matter radioactivity is intense and clearly exceeds radioactivity in adjacent white matter.

Some scans may be difficult to interpret due to image noise, atrophy with a thinned cortical ribbon, or image blur. For cases in which there is uncertainty as to the location or edge of gray matter on the PET scan and a co-registered computerized tomography (CT) image is available (as when the study is done on a PET/CT scanner) the interpreter should examine the CT image to clarify the relationship of the PET radioactivity and the gray matter anatomy.

Figures 1, 2, and 3 provide examples of negative and positive scans. Figure 1 demonstrates varying degrees of normal gray-white contrast (negative) and examples where gray-white contrast has been lost (positive). Figure 2 illustrates typical features of a negative scan, while Figure 3 shows the loss of gray-white contrast in different brain regions of a positive scan.

[figure not shown]

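### Secondary objective 3 and endpoint 3 name amyloid plaque size and number, which two florbetapir PET scans, each read as positive or negative, cannot measure

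*Combined protocol and SAP*

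**What the plan says.** Objective 3 in section 2.2 sets out to relate neurocognitive and quality-of-life scores to "changes in amyloid plaque size, number and location". Endpoint 3 in section 2.4 lists "amyloid number, size and location and changes after treatment" and omits the word plaque.

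The data source is one Amyvid scan before treatment and one at 4 months (sections 3.6 and 3.11). Both are 10-minute images reconstructed with "resulting transaxial pixel sizes between 2 and 3 mm". Section 3.6 gives the read: "Images are designated as positive or negative by comparing the radioactivity in cortical gray matter with activity in the adjacent white matter". For the second scan, section 3.11 says only "Analysis will be carried out as previously described". The protocol defines no uptake ratio, regional score or other graded measure.

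The prescribing information in Appendix VII says that the read estimates "neuritic plaque density, not to make a clinical diagnosis" (label section 2.4). The usual positive pattern is "Two or more brain areas (each larger than a single cortical gyrus) in which there is reduced or absent gray-white contrast".

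**The concern.** Plaque number and size are histology quantities. The mouse work in sections 1.5.1 and 1.5.2 obtained them from stained brain sections. The clinical objective carries the same words over to a scan that measures tracer signal at a much coarser scale.

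Followed as written, the endpoint has no variable for plaque size and none for a count of plaques. The read that is planned would not supply location or degree of change either. The analyst would have to choose a substitute after the scans are in. The wording also leaves room to report lower uptake in the terms of the mouse findings, and the scan could not support a statement about plaque size.

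**Working it through.** The plan gives no figure of its own on this point, so the check compares scales and then compares passages.

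**Inputs**
- Pixel edge: 2 to 3 mm, or 2000 to 3000 micrometres (sections 3.6 and 3.11).
- Plaque size in mice: section 1.5.2 reports "Average plaque size also decreased following irradiation from 42.95" to 14.52. The unit is printed as μM. I read it as micrometres and treat size as diameter.
- Plaque size in humans: not in the documents. I assume 100 to 200 micrometres.

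**Formula:** pixel edge divided by plaque diameter.

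| Plaque diameter (micrometres) | 2 mm pixel | 3 mm pixel |
|---|---|---|
| 42.95 (unirradiated mice) | 2000/42.95 = 46.6 | 3000/42.95 = 69.8 |
| 14.52 (irradiated mice) | 2000/14.52 = 137.7 | 3000/14.52 = 206.6 |
| 100 (assumed) | 20 | 30 |
| 200 (assumed) | 10 | 15 |

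In every row the pixel is at least ten times as wide as a plaque, so single plaques can be neither sized nor counted.

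**Where plaque counts and sizes come from.** Every one reported in the documents comes from stained tissue: mouse brain sections in 1.5.1 and 1.5.2, and post-mortem silver-stained slides in label section 14. None was made on a PET image.

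**What the planned read can register.** By the label, a negative scan corresponds to sparse or no plaques and a positive scan to moderate or frequent plaques. Label Table 5 gives counts of 6-19 for moderate and 20 or more for frequent. A patient who moved from frequent to moderate would therefore still be expected to read positive, and the planned variable would show no change. One positive or negative result per scan also carries no regional information.

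**The case against.** Four points on the other side deserve weight.

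- **Number.** A reader might infer that plaque number can never be obtained in any sense. The documents do not support that. The label presents the scan as an estimate of plaque density, and Table 5 ties image results to count categories. What stands is narrower: the scan does not count individual plaques, and the planned read collapses density to two classes.
- **Wording of endpoint 3.** Without the word plaque, number and size could mean the number and extent of positive areas, in line with the label's positivity rule. That reading is possible, but no such measure is defined, and objective 3 says plaque explicitly. It is also tempting to say that exactly two of the three named quantities lack data. That count is not secure: on this reading all three are image quantities, while under the binary read location is not recorded either.
- **Scale.** One could go on to calculate how many plaques fit in a voxel. The documents do not support such a figure. They give only the transaxial pixel size, and label section 14 puts post-mortem cortical amyloid burden at 0 to 9%, so a voxel cannot be treated as solid plaque. The linear ratios suffice.
- **Importance.** Section 3.1 describes a descriptive pilot, and this is its third secondary objective. No sample size rests on plaque size or number, and stopping rule 4 in section 3.12 speaks of amyloid, not of either quantity. No passage plans to report smaller plaques, so that risk is conjecture. This limits the severity. A descriptive summary still needs a variable that the study measures, and section 3.1 gives the pilot the task of finding what to modify for a larger trial.

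**Conclusion.** The concern holds in this form: the planned scans cannot deliver plaque size or a count of individual plaques, and the planned read delivers neither location nor graded change. The scale gap is about 47 to 70 at the unirradiated mouse figure, and 10 to 30 at the assumed human range. It rests on reading the printed unit as micrometres and size as diameter, and on the assumed human range. The conclusion is the same throughout that range, and the comparison of passages supports it independently.

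The point should be corrected before the imaging is analysed. It concerns a secondary objective and its endpoint, and leaves the primary safety endpoint untouched.

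**What to change.** In objective 3 (section 2.2) and endpoint 3 (section 2.4), replace plaque size and number with change from baseline to 4 months in global and regional cortical florbetapir uptake. Define it as an SUV ratio in cortical regions named in the protocol before analysis; those regions then supply location. Label section 12.2 already describes automated SUV assessment in pre-specified regions and a cortical-to-cerebellar ratio. The planned field of view includes the cerebellum, so the scans already scheduled should serve.

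Three additions are needed.
- **Reference region.** The target in section 3.8.2 is the whole brain, so the cerebellum is irradiated too. A change in its uptake would move the ratio with no cortical change. Report the change in reference-region uptake beside the ratio, or add a sensitivity analysis with another reference region. Any other brain region is also irradiated, so this tests dependence on the choice and does not provide an untreated control.
- **Language.** State that results will be described as tracer uptake, not as plaque number or size.
- **Limitation.** State that, by the label's limitations of use, the scan is not established for monitoring response to therapy.

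The cost is a wording change and some additional image analysis, with no new scan or visit. The downside is a narrower imaging claim than the one made from the mouse work.
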